9 SCREENING, REGISTRATION, AND ON-STUDY TESTS AND PROCEDURES

In addition to assessment for the **primary** endpoint (VO₂peak) by cardiopulmonary exercise testing (CPET), **secondary** and **exploratory** assessments for functional capacity, quantitative skeletal muscle function, metabolic, patient-reported outcomes, PSA, and metabolomics endpoints will occur throughout the study as specified below in the Schedule of Events.

The important time periods during the study include:

- **Screening** on Day -42 to randomization
- **Exercise Testing on Day -30 to randomization**
- **Randomization on Day -14 to Day 1, but after exercise testing (specifically, CPET) is complete**
- **Lead-In** of Usual Care (UC) or Exercise Training starting on Day 1
- **Treatment Period 1:** Enzalutamide + ADT with either UC or Exercise Training from Day 29 to 113
- **Treatment Period 2:** Enzalutamide + ADT from Day 114 to 252
- **End of treatment/Safety Follow-Up** within 30 days after the last dose of enzalutamide or prior to initiation of cytotoxic or investigation therapy, whichever occurs first

All subjects will receive treatment with ADT + enzalutamide for 32 weeks.

In addition, subjects randomized to Exercise Training (Arm B) will undergo a 16 week combined aerobic and resistance exercise training program, including a 4 week Lead-In before starting therapy with ADT + enzalutamide and during the first 12 weeks of therapy with ADT + enzalutamide.

SCHEDULE OF EVENTS

Phase		Screen	Baseline Exercise Testing ^{c,p}	4 Week Lead-In ^p		Treatment Period 1: Enzalutamide + ADT +/- Exercise Training				Treatment Period 2: Enzalutamide + ADT and Safety Follow-up	Unscheduled Visit ^a
				2	3	4					
Clinic Visit Number		1				2	3	4	5 (EOT) SEE NOTE		
Day		-42 to randomization	-30 to randomization	1 ^q	22	29	57	64	113	252	
Week		-6 to -1		1	4	5	9	10	17 ^a	37 ^a	
Window (Days)		NA		NA	+6	±3	±7	±3	±7	-7, +30	NA
General Evaluations	See Section										
Informed Consent ^b	9.2.1	X									
Eligibility Criteria	8	X									
Medical History	9.12.1	X									
Randomization ^c	6.1.4			X ^c							
Physical Exam ^d	9.12.2	X				X	X		X	X	X
Height, Weight, BMI	9.12.2	X				X	X		X	X	X
Vital Signs ^e	9.12.2	X				X	X		X	X	X
Performance Status (ECOG) ^f	App. A	X				X	X		X	X	X
Concomitant Medications	6.1.3	X				X	X		X	X	X
Adverse Events ^g	10	X				X	X		X	X	X
Laboratory Evaluations											
CBC with platelets ⁱ	9.1-9.7	X ⁱ				X	X		X	X	X ^h
Serum Chemistry ⁱ	9.1-9.7	X ⁱ				X	X		X	X	X ^h

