9.5 Lead-In Period

Subjects will be randomized to usual care or exercise training up to 14 days prior to Day 1, but only after eligibility is confirmed and baseline exercise testing (specifically, CPET) has been performed. See **Sections 6.1.4** and **9.4** for randomization details. See also **Schedule of Events**, above.

Arm A, ENZ – ADT plus Usual Care: Subjects randomized to usual care will be asked not to make any changes in their physical activity beginning on Day 1. These subjects will start ENZ – ADT on Day 29 (week 5) after the 4 week lead-in period. This delay is felt to be insignificant from a clinical perspective. While two Phase III studies are currently examining this question (NCT00439751; NCT00110162), the delay in initiation of ADT in these studies is much longer than 4 weeks. There is currently no evidence that a delay, especially one as short as 4 weeks, in starting ADT in men with non-metastatic prostate cancer, affects outcomes.⁸⁸

Arm B, ENZ – ADT plus Exercise Training: Subjects randomized to exercise training will begin the exercise training program detailed below beginning on Day 1. The goal for the ENZ-ADT plus exercise training will be 3 supervised exercise sessions per week at an intensity between 50 and 100% of the individually determined exercise capacity (at baseline) for aerobic training and an intensity between 60% and 80% of one-repetition maximum (1-RM) for resistance training for 30-90 minutes/session. The exercise training intervention is designed such that participants begin exercising at a low intensity (~50%-60% VO₂peak) that is subsequently increased to more moderate to vigorous intensity (~70%-80% VO₂peak) when appropriate. All interventions will be individually tailored to each subject following the principles of aerobic or resistance training prescription guidelines for adults as recommended by the American College of Sports Medicine (ACSM).⁸⁹ All exercise sessions will also be performed in a supervised setting with one-on-one supervision by certified exercise physiologists, physical therapists, exercise physiology students under the supervision of an ACSM-certified exercise physiologist, or trained designee. The exercise prescription for each subject will be created centrally by either [name] group at MSKCC or the CPX Lab at Duke based on both the interpretation of the CPET plus Muscular Strength/1-RM data and a standardized template, within 24-48 hours of these tests.

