9.6 Treatment Period 1: ENZ-ADT plus either Usual Care or Exercise Training

Arm A, ENZ – ADT plus Usual Care: Beginning on Day 29 (week 5), subjects will be treated with androgen deprivation therapy (ADT) per standard of care (orchiectomy, GnRH agonist, or GnRH antagonist to maintain total testosterone <50 ng/dl for the remaining 32 weeks of the study). In addition, subjects will take enzalutamide (ENZ) 160 mg by mouth daily for the remaining 32 weeks of the study. The dosing of both the GnRH agonist and enzalutamide (160 mg daily) is the standard-of-care dosing. The treatment duration of approximately 8 months was selected to achieve maximal efficacy while minimizing toxicity and is based on intermittent hormonal therapy regimens studied in Phase III clinical trials.^{22,23} Concomitant medication will be evaluated at every clinic visit during enzalutamide therapy. Concomitant medications include all vitamins, herbal remedies, over the counter, and prescription medications.

Arm B, ENZ – ADT plus Exercise Training: Beginning on Day 29 (week 5), Subjects randomly allocated to this group will receive the same ADT-ENZ regimen as described above. In addition, subjects will continue the defined exercise training initiated during the Lead-In Period for a total of 16 weeks (through Day 113, week 17).

The window is ± 7 days for this period, EXCEPT Day 29 (week 5) which has a window of ± 3 days. See **Schedule of Events**, above.

Subject data to be collected during Treatment Period 1 includes:

- Physical Exam
- Height, Weight, BMI
- Vital Signs
- Performance Status (ECOG)
- Concomitant Medications
- Adverse Events
- CBC with Platelets (hemoglobin, hematocrit, platelet count, white blood cell count, total [absolute] neutrophils)
- Serum Chemistry (sodium, potassium, chloride, total CO₂ [bicarbonate], calcium, BUN, creatinine, glucose, albumin, total bilirubin, total protein, alkaline phosphatase, AST, ALT)
- Testosterone (Day 57 and 113)
- PSA
- CPET (Day 29 and Day 113)
- Chair Stand (Day 113)
- Timed Up and Go (Day 113)
- 6 Minute Walk Distance (Day 113; **Duke patients only**)
- Muscular Strength (*at least 24 hours before or after CPET on Week 4, Week 10 (not in conjunction with CPET) and week 17 in treatment period 2*)
- Muscle CSA (MRI; Day 113; **protocol v1-v15 only**)
- Muscular Endurance (*must be at least 24 hours before or after CPET to allow for adequate recovery on week 4, week 10 (not in conjunction with CPET) and week 17 in treatment period 2*)

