10 SAFETY MONITORING AND REPORTING

The PI is responsible for the identification and documentation of adverse events and serious adverse events, as defined below. At each study visit, the PI or designee must assess, through non-suggestive inquiries of the subject or evaluation of study assessments, whether an AE or SAE has occurred.

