10.1 Adverse Events

An adverse event (AE) is any untoward medical occurrence in a subject undergoing a study procedure/intervention and/or receiving study drug; which may or may not have a causal relationship with study procedures, interventions or treatments. For this protocol, the definition of AE also includes worsening of any pre-existing medical condition. An AE can therefore be any unfavorable, unintended or worsening sign or symptom (including an abnormal laboratory finding, or disease temporally associated with exercise testing for both arm A and arm B; exercise training for arm B; and/ or related to the use of enzalutamide. Abnormal laboratory findings without clinical significance (based on the PI's judgment) should not be recorded as AEs. But laboratory value changes that require therapy or adjustment in prior therapy are considered adverse events.

Research exercise-related adverse events will be collected from the baseline exercise testing to the End of Study visit (as defined in **Section 9.8**) for all subjects (Except anticipated AEs-see section 10.1.2). All subjects will have enzalutamide related adverse events collected from the start of study drug on week 5, day 29 through the Safety Follow-up visit.

Serious adverse events that are related to study exercise procedures (CPET, 1RM, Chair testing, etc) are recorded from the time the informed consent form is signed until the Safety Follow-Up visit (withdrawal or screen failure). All SAEs will be collected regardless of attribution starting once the patient takes his first dose of study drug through the Safety Follow-Up visit. All AEs and SAEs must be recorded in the subject medical record and adverse events case report form.

AEs will be assessed according to the CTCAE version 4.0. If CTCAE grading does not exist for an AE, the severity of the AE will be graded as mild (1), moderate (2), severe (3), life-threatening (4), or fatal (5).

Attribution of AEs will be indicated as follows:

- Definite: The AE is clearly related to the study drug and/or exercise training and/or exercise testing
- Probably: The AE is likely related to the study drug and/or exercise training and/or exercise testing
- Possible: The AE may be related to the study drug and/or exercise training and/or exercise testing
- Unlikely: The AE is doubtfully related to the study drug and/or exercise training and/or exercise testing

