For analysis of metabolomics, PCA analysis will be used to reduce the large number of correlated factors into a smaller number of dimensions. Unless otherwise noted, all analyses will be done separately for the usual care and exercise groups. Of primary interest is the association of metabolomic biomarkers with changes in both VO₂peak and HOMA-IR. Changes in metabolite concentrations and VO₂peak or HOMA-IR will be compared between the usual care and exercise groups using ANOVA. Correlation analysis and linear regression will be used to describe the relationship between metabolomics biomarker changes and VO₂peak or and HOMA-IR. Nominal statistical significance will be defined as p<0.05.

In addition, the maximum PSA change from baseline in each patient will be described using waterfall plots. The PSA response rate, defined as the proportion of men with a ≥80% decline in PSA from baseline, will be reported for each arm. The median decrease in PSA will also be reported for each arm.

Sensitivity analyses will be performed repeating primary endpoint and key secondary endpoint analyses using Last Value Carried Forward (LOCF) methods. The intent of this sensitivity analysis is to assay the robustness of results observed in the modified ITT population.

Adjustment for multiple comparisons is not planned for secondary or exploratory measures.

Rates of adverse events, classified by CTCAE v4.0, will be displayed by body system and preferred term for each arm.

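### Adverse event rates by arm may be ascertained unequally: Arm B's supervised sessions give extra chances for low-grade events to come to light, and the plan does not record how an event was found

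*Combined protocol and SAP*

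**What the plan says.** **AE enquiry.** Section 10 makes the investigator or a designee responsible: "At each study visit, the PI or designee must assess, through non-suggestive inquiries of the subject". It sets no different rule by arm. The Schedule of Events in Section 9 has one AE row for both arms. After randomization it is marked on Days 29, 57, 113 and 252, and at unscheduled visits.

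**Contact through training.** Section 9.5 sets a goal for Arm B of "3 supervised exercise sessions per week", with "one-on-one supervision by certified exercise physiologists" or other listed staff. Under Section 9.6 these men "will continue the defined exercise training initiated during the Lead-In Period for a total of 16 weeks".

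**What counts and when.** The AE definition in 10.1 includes "disease temporally associated with exercise testing for both arm A and arm B; exercise training for arm B", and 10.1 requires every AE and SAE to be entered in the medical record and the AE case report form. Exercise-related AEs are collected from baseline in all men; other AEs only from the start of study drug (Section 9, footnote g). Section 10.1.2 leaves four transient expected effects unrecorded: muscle soreness, joint pain, lower back pain and leg cramps.

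**Use.** Section 5 lists the AE rate in each arm under the objective on safety, feasibility and acceptability of exercise training. Section 12.5 says: "Rates of adverse events, classified by CTCAE v4.0, will be displayed by body system and preferred term for each arm". The trial is open label (6.1.4). No section states whether a training session is a study visit for AE purposes, whether trainers ask about or pass on AEs, or whether the source of an AE is recorded.

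**The concern.** The scheduled enquiries are equal, but the chances for an event to reach staff are not. A man in Arm B who is dizzy, has a headache or is briefly more tired will usually be face to face with study personnel within two or three days. A man in Arm A with the same event may next be asked about it weeks later; the longest gap between marked AE assessments up to week 17 is the 8 weeks from Day 57 to Day 113. If the event has resolved, he may not mention it.

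This differs from the question of which AEs are attributable to exercise. It applies equally to enzalutamide-related symptoms after Day 29, which should occur at similar rates in the two arms if exercise has no effect on them.

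At stake is the reading of the AE table. If Arm B shows more low-grade AEs, exercise could look harmful when it was only watched more closely. If exercise reduces reports of fatigue or generalized muscle weakness, the AEs of special interest in 10.1.1, better detection in Arm B could mask part of that in the AE display. Without a source for each event, neither possibility can be examined afterwards.

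**Working it through.** The plan states no session total, AE rate by arm or detection rate, so there is no figure of its own to reproduce on this point.

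**1. Contacts**
- Sessions (9.5, 9.6): 3 × 16 = 48. Lead-in: 3 × 4 = 12. From Day 29: 3 × 12 = 36. These are goals, not attendance.
- Marked AE assessments after randomization and up to Day 113: Days 29, 57 and 113, so 3 in each arm.
- Strength and endurance tests at Day 22 and Day 64 are not limited to one arm in the text. The AE row is blank on both days.

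| Counting rule | Arm B | Arm A |
|---|---|---|
| Only marked AE assessments | 3 | 3 |
| Sessions also count | 48 + 3 = 51 | 3 |
| Sessions and Day 22/64 tests also count | 48 + 5 = 53 | 5 |

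The text does not say which row applies.

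**2. Short events missed in Arm A from Day 29**

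Assume that onset is uniform over Days 30 to 113 (84 days), and that a resolved event is reported only if it falls in the R days up to and including a contact. R is assumed; the documents give no recall figure.

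| R (days) | Asked at Days 57 and 113 | Also at Day 64 |
|---|---|---|
| 14 | 56/84 = 67% | 49/84 = 58% |
| 28 | 28/84 = 33% | 21/84 = 25% |
| 42 | 14/84 = 17% | 7/84 = 8% |
| 56 | 0% | 0% |

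The window starts at Day 29 because non-exercise AEs are not collected during the lead-in.

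**3. Effect on the recorded ratio**

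Let r be the chance that an event is picked up at the common visits, and s the chance that an event missed there is recorded through a session. With equal true rates, the recorded ratio B/A = [1 − (1 − r)(1 − s)] / r. Example: r = 0.7 and s = 0.25 give (1 − 0.3 × 0.75)/0.7 = 0.775/0.7 = 1.11.

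| r | s = 0 | s = 0.25 | s = 0.5 | s = 1 |
|---|---|---|---|---|
| 0.5 | 1.0 | 1.25 | 1.50 | 2.00 |
| 0.7 | 1.0 | 1.11 | 1.21 | 1.43 |
| 0.9 | 1.0 | 1.03 | 1.06 | 1.11 |
| 1.0 | 1.0 | 1.0 | 1.0 | 1.0 |

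**4. Scale against chance**

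Take 34.3% as a true rate in both arms. This is the fatigue frequency that Section 4.3 cites from the enzalutamide monotherapy study, used here only for scale. With 20 men per arm, the standard error of the difference is √(2 × 0.343 × 0.657/20) = 0.150, and the 95% half-width is 1.96 × 0.150 = 29 points. If every event were short and Arm A missed 25% of them, it would show 34.3 × 0.75 = 25.7%. That is a gap of 8.6 points, or 0.086 × 20 = 1.7 men: visible in a table, but well inside chance variation.

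**The case against.** **A stronger reading.** A reader might infer that Arm B is observed 48 times against 3, so that the AE comparison is biased against exercise through observation alone. The documents do not support that.

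- Arm B has the same three scheduled AE assessments as Arm A, and no section makes a training session an AE enquiry. Setting 48 against 3 compares contacts with enquiries.
- If unmarked contacts count in Arm B, the Day 22 and Day 64 tests should count too. Unscheduled visits for AEs are open to both arms.
- The direction is not fixed. Leaving transient soreness, joint pain, back pain and cramps unrecorded can lower Arm B's count, although the operative sentence in 10.1.2 names only the cardiopulmonary exercise test (CPET) under a heading that also covers training. Training-related AEs can arise only in Arm B, which is a difference other than observation.
- Fatigue and strength are also measured on the same schedule in both arms, by FACIT-F and the one-repetition maximum. A benefit on either would not rest on AE reports.
- No test of AE rates is planned.

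All of this stands, and it limits the point to a risk of unknown size.

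**What it does not remove.** Concern does not depend on sessions being formal enquiries: once an AE comes to staff attention, 10.1 requires it to be recorded. The four excluded effects do not include fatigue, generalized weakness, dizziness, falls or headache; for those, extra contact can raise Arm B's count and has no evident way to lower it. The plan's silence also leaves the two sites free to follow different practices.

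**Conclusion.** The by-arm AE rates may be ascertained unequally, and the plan as written gives no means of checking. The firm facts are equal scheduled enquiry in both arms, a goal of about 48 one-on-one sessions in Arm B only (about 36 after Day 29), a duty to record AEs, and no provision for noting how an AE was found.

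The size cannot be derived from the documents. Under the assumed values of r and s the recorded ratio runs from 1.0 to 2.0, and it is exactly 1.0 if sessions yield no reports or recall at visits is complete. The calculations assume equal true rates, full attendance and events that resolve between visits. They stop at Day 113, whereas the AE display runs to the Day 252 visit. SAEs, laboratory-detected events and persistent events are little affected.

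Because the rates are displayed without a test and the primary endpoint is not involved, this is an inexpensive improvement to the interpretability of the safety display. It is not evidence that the display will be biased.

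**What to change.** 1. State in Section 10 whether training sessions are AE enquiry points and how an event noticed at a session reaches the AE form, identically at both sites.
2. Add one field to the AE form for how the event was found: scheduled visit, exercise session, or spontaneous/unscheduled.
3. Keep the full by-arm AE display in 12.5. Beside it, add a by-arm table limited to events elicited by the same non-suggestive enquiry at the common visits (Days 29, 57, 113 and 252), with each man asked about the whole interval since his last visit. Show Arm B events found only at sessions separately. The new table should not replace the full one, since that would drop real Arm B events from the main safety display.

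**Cost.** One form field and one extra table, with no added visits. Recording and expedited reporting do not change.

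**Limits.** Men were already enrolled before protocol v16 (Section 9, footnote s), so the source may be missing for AEs already recorded. Men in Arm B who discussed an event at a session may recall it better at the next visit, so some imbalance may remain in the like-for-like table.

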10.1 Adverse Events

An adverse event (AE) is any untoward medical occurrence in a subject undergoing a study procedure/intervention and/or receiving study drug; which may or may not have a causal relationship with study procedures, interventions or treatments. For this protocol, the definition of AE also includes worsening of any pre-existing medical condition. An AE can therefore be any unfavorable, unintended or worsening sign or symptom (including an abnormal laboratory finding, or disease temporally associated with exercise testing for both arm A and arm B; exercise training for arm B; and/ or related to the use of enzalutamide. Abnormal laboratory findings without clinical significance (based on the PI's judgment) should not be recorded as AEs. But laboratory value changes that require therapy or adjustment in prior therapy are considered adverse events.

Research exercise-related adverse events will be collected from the baseline exercise testing to the End of Study visit (as defined in **Section 9.8**) for all subjects (Except anticipated AEs-see section 10.1.2). All subjects will have enzalutamide related adverse events collected from the start of study drug on week 5, day 29 through the Safety Follow-up visit.

Serious adverse events that are related to study exercise procedures (CPET, 1RM, Chair testing, etc) are recorded from the time the informed consent form is signed until the Safety Follow-Up visit (withdrawal or screen failure). All SAEs will be collected regardless of attribution starting once the patient takes his first dose of study drug through the Safety Follow-Up visit. All AEs and SAEs must be recorded in the subject medical record and adverse events case report form.

AEs will be assessed according to the CTCAE version 4.0. If CTCAE grading does not exist for an AE, the severity of the AE will be graded as mild (1), moderate (2), severe (3), life-threatening (4), or fatal (5).

Attribution of AEs will be indicated as follows:

- Definite: The AE is clearly related to the study drug and/or exercise training and/or exercise testing
- Probably: The AE is likely related to the study drug and/or exercise training and/or exercise testing
- Possible: The AE may be related to the study drug and/or exercise training and/or exercise testing
- Unlikely: The AE is doubtfully related to the study drug and/or exercise training and/or exercise testing
- Unrelated: The AE is clearly NOT related to the study drug and/or exercise training and/or exercise testing

10.1.1 AEs of Special Interest

“Fatigue” and “generalized muscle weakness” (regardless of site) are AEs of special interest. Care should be taken to appropriately identify, grade, and note the attribution of these AES throughout the study. However, there is no special reporting requirement for these AEs.

